## 6.2 Secondary Efficacy

The secondary endpoint of this study is the modified change in 6-minute walk test (6MWT) distance score.

The baseline 6MWD result is the average of Screening and Day 1 6MWT values.

Pulse oximetry at resting and the end of the 6MWT will be summarized using summary statistics, at described in Section 3.1.

The change from baseline in 6MWT will be analyzed using the same MMRM model used for the primary efficacy endpoint. Analysis visits 0, 4, 8 and 12 will be used. The pairwise dose group comparisons with placebo will be estimated using the difference in adjusted means and 95% CI for the difference in changes from baseline to Week 12.

#### 6.3 Exploratory Efficacy

Summary statistics and 95% confidence intervals for treatment differences in mean change from baseline, using the same MMRM model used for the primary and secondary endpoints, will be provided for all exploratory endpoints unless otherwise noted. P-values will be provided for descriptive purposes only.

For parameters having repeated measurements within an analysis visit during the maximal and submaximal exercise test, the MMRM code should incorporate the analysis visit and assessment time (during the exercise test) in the analysis:

```
Proc Mixed data=x order=data;
Class patno trt week;
model resp = trt*time*week /s;
Repeated time*week / sub = patno type = un;
```

```
lsmeans trt*time*week / diff cl alpha=0.05;
Run;
```

For blood lactate measurements during the submaximal exercise test, the repeated measures model will incorporate baseline resting blood lactate as a covariate:

```
Proc Mixed data=x order=data;
  Class patno trt week;
  model resp = trt*time*week baseline_resting_lactate /s;
  Repeated time*week / sub = patno type = un;
  lsmeans trt*time*week / diff cl alpha=0.05;
  Run:
```

As with the primary and secondary endpoints, exploratory endpoints will be analyzed using individual doses of RTA 408 versus placebo pooled. A separate model that does not pool the RTA 408 doses will be used to obtain pairwise differences for each dose level versus pooled placebo.

For parameters having repeated measurements within an analysis visit during the maximal and submaximal exercise test, the change from resting (delta) for parameters measured at resting and a certain timepoint during the maximal or submaximal exercise test will be reported as:

Delta = [Parameter at Y min] – [Parameter at resting]

In the maximal exercise test, laboratory measurements may be measured at resting, at the end of the maximal exercise test, 5 min after the end of the maximal exercise test, and 10 min after the end of the maximal exercise test.

In the submaximal exercise test, efficacy and laboratory measurements are recorded at resting, at 10 min, 20 min, and 30 min.

The change from baseline is defined for parameters measured at resting and a certain timepoint during the maximal of submaximal exercise test is defined as:

Change from Baseline in Delta= [Parameter at Y (At Visit X) - Parameter at resting(At Visit X)] - [Parameter at Y min (At Baseline) - Parameter at resting(At Baseline)]

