#### 6.3.3 Submaximal Exercise Testing Parameters

The following parameters are assessed at resting, at 10 minutes, 20 minutes, and 30 minutes during the submaximal exercise test.

Table 4: Submaximal Exercise Testing Parameters

Parameter	At Rest (Prior to Test)	10 minutes	20 minutes	30 minutes (End of Test)
Borg		X	X	X
Leg Effort Rating of Perceived Exertion		X	X	X
Heart Rate ( bpm ) a	X	X	X	X
Carbon Dioxide Production (VCO 2 ) ( mL/kg/min ) a,b	X	X	X	X
Oxygen Comsumption (VO 2 ) ( mL/kg/min ) a,b	X	X	X	X
Expired Air Gas Volume (VeBTPS) ( L/min ) a	X			X
Cardiac Output ( L/min ) a	X			X
Arteriovenous Oxygen Difference (a-VO 2diff ) ( mLO2/dlQ ) a	X			X
Respiratory Exchange Ratio a	X			X
Starting Workload ( W )	X			
Exercise Duration ( min )				X
Final Workload ( W )				X

<sup>aObserved values and difference between resting and 30 minutes for these parameters will be summarized at baseline and at each timepoint. For parameters measured at resting and at the end of the submaximal exercise test (for patients who complete 30 minutes of the test), the change from resting and the change from baseline should be calculated.

The change from resting (delta) for parameters measured at resting and at the end of the submaximal exercise test is defined as:

Delta = Parameter at 10, 20, or 30 min - Parameter at resting

The change from baseline is defined for parameters measured at resting and at the end of the submaximal exercise test is defined as:

Change from baseline in Delta= [Parameter at Y min (At Visit X) - Parameter at resting(At Visit X)] - [Parameter at Y min (At Baseline) - Parameter at resting(At Baseline)]

Summary statistics at resting, at 10 minutes, 20 minutes, and 30 minutes will be provided.

b Analysis of VO2 and VCO2 will be performed using adjustments for weight at the visit week in which the submaximal exercise test was performed

The MMRM analysis should incorporate the visit and time (during the exercise test) interaction for change from baseline heart rate, as described in Section 6.3.

The change from baseline resting heart rate is defined as:

Change from baseline in Heart Rate= [Heart Rate at Y min (At Visit X) - Heart Rate at resting(At Visit X)] - [Heart Rate at Y min (At Baseline) - Heart Rate at resting(At Baseline)]

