#### 6.3.4 Submaximal Exercise Testing Laboratory Parameters

The following laboratory parameters are assessed at resting, at 10 minutes, 20 minutes, and 30 minutes during the submaximal exercise test.

Parameter	At Rest (Prior to Test)	10 minutes	20 minutes	30 minutes (End of Test)
Blood Glucose ( mg/dL ) a	X	X	X	X
Blood Lactate ( mM ) a	X	X	X	X
Blood Pyruvate ( mM )a	X	X	X	X

aObserved values and difference between resting and 30 minutes for these parameters will be summarized at baseline and at each timepoint. For parameters measured at resting and at the end of the submaximal exercise test (for patients who complete 30 minutes of the test), the change from resting and the change from baseline should be calculated.

The change from resting (delta) for parameters measured at resting and at the end of the submaximal exercise test is defined as:

Delta = Parameter at 10, 20, or 30 min - Parameter at resting

The change from baseline is defined for parameters measured at resting and at the end of the submaximal exercise test is defined as:

Change from baseline in Delta= [Parameter at Y min (At Visit X) - Parameter at resting(At Visit X)] - [Parameter at Y min (At Baseline) - Parameter at resting(At Baseline)]

Summary statistics at resting, at 10 minutes, 20 minutes, and 30 minutes will be provided.

The MMRM analysis of change from baseline blood lactate should incorporate the visit and time (during the exercise test) interaction for submaximal exercise testing laboratory parameters, as described in Section 6.3.

The change from resting blood lactate is defined as:

 Change from baseline in Blood Lactate= [Blood Lactate at Y min (At Visit X) - Blood Lactate at resting(At Visit X)] - [Blood Lactate at Y min (At Baseline) - Blood Lactate at resting(At Baseline)] Analysis visits 0, 4, 8 and 12 will be used. The pairwise dose group comparisons with placebo will be estimated using the difference in adjusted means and 95% CI for the difference in changes from baseline to Week 12.

Page 28 of 38

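### The submaximal lactate and heart-rate models leave out the baseline exercise rise, so their exploratory dose-versus-placebo intervals are wider than they need to be

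*SAP*

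**What the plan says.** **Lactate.** SAP 6.3 states: "For blood lactate measurements during the submaximal exercise test, the repeated measures model will incorporate baseline resting blood lactate as a covariate". It gives the statement "model resp = trt*time*week baseline_resting_lactate /s". SAP 6.3.4 says what is modelled: "The MMRM analysis of change from baseline blood lactate should incorporate the visit and time (during the exercise test) interaction". Its formula takes the lactate rise from rest to minute Y at the visit and subtracts the baseline rise, "Blood Lactate at Y min (At Baseline) - Blood Lactate at resting(At Baseline", inside closing brackets.

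**Heart rate.** SAP 6.3.3 says: "The MMRM analysis should incorporate the visit and time (during the exercise test) interaction for change from baseline heart rate". It refers to Section 6.3 for the model, where the generic statement is "model resp = trt*time*week /s", with no covariate. The heart-rate response has the same double-difference form.

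**Data available.** The SAP schedule places the submaximal test on Day 1 (before the first dose), at Visit 6 (Week 4) and at Visit 11 (Week 12). SAP 6.3 records values at rest and at 10, 20 and 30 minutes.

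**Covariates elsewhere.** SAP 3.3 excludes covariates from the primary analysis of Part 1 because dose groups are small. It does not mention the exploratory models. For the Part 2 primary analysis, Protocol 14.3.2 adjusts peak work for its own baseline.

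**The concern.** When a response is a change from baseline, the covariate that usually buys precision is the baseline value of the same quantity. Here that is the baseline rise at the same minute. The plan computes it to form the response but does not adjust for it. The lactate model adjusts for resting lactate, which is only one component of the baseline rise. The heart-rate model adjusts for nothing.

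Two things follow. First, the baseline noise enters each dose-versus-placebo estimate at full weight. Second, a chance difference in baseline rise between a dose group of 6 and pooled placebo carries into that estimate through regression to the mean. Submaximal lactate is listed as a pharmacodynamic endpoint in the protocol synopsis, and dose groups are small, so interval width matters for reading these results.

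**Working it through.** **The plan's own figure.** The documents give no power or correlation for submaximal lactate or heart rate. Their only power figure is about 80% for Part 2 peak work (Protocol 14.1): difference 0.28 W/kg, SD 0.28, correlation 0.20, and 14 versus 7 patients after dropout. Averaging two post-baseline visits gives SD = 0.28 × √((1 + 0.20)/2) = 0.2169. Then 0.28 / (0.2169 × √(1/7 + 1/14)) = 2.79, and the power is Φ(2.79 − 1.96) = 79.6%. The figure reproduces. It concerns another measure and does not bear on this point.

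**Setup.** Let D be the value at minute Y minus rest, with equal variance (set to 1) at baseline and visit, and let ρ be the baseline-to-visit correlation of D. ρ is an assumption, shown as a range. The groups are 6 on a dose and up to 16 on pooled placebo (8 cohorts of 6 + 2; SAP 1.2, 1.3 and 3.1).

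**Heart rate.**
- Residual variance as planned, no covariate: 2(1 − ρ).
- Residual variance adjusted for baseline D: 1 − ρ².
- Ratio: (1 + ρ)/2.
- SE of a single-visit contrast: √variance × √(1/6 + 1/16), where the second factor is 0.479.
- Typical carry-over of chance imbalance in the unadjusted estimate: (1 − ρ) × 0.479, in SDs of D.

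| ρ | Variance ratio | CI width ratio | SE planned → adjusted (SD units) | Typical carry-over (SD units) |
|---|---|---|---|---|
| 0.2 | 0.60 | 0.77 | 0.606 → 0.469 | 0.38 |
| 0.5 | 0.75 | 0.87 | 0.479 → 0.415 | 0.24 |
| 0.8 | 0.90 | 0.95 | 0.303 → 0.287 | 0.10 |
| 0.9 | 0.95 | 0.97 | 0.214 → 0.209 | 0.05 |

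**Cost of estimating the slope.** The variance is multiplied by about 1 + 1/(N − g − 2), for N patients in g groups.
- 64 patients, 9 groups: 1 + 1/53, about 2%. The gain disappears at ρ = 2 × 53/54 − 1 = 0.96.
- 32 patients, 5 groups: 1 + 1/25 = 4%. The gain disappears at ρ = 2 × 25/26 − 1 = 0.92.
- 16 patients, 5 groups (3 per dose, 4 placebo): 1 + 1/9 = 11%. The gain disappears at ρ = 2 × 9/10 − 1 = 0.80.

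**Lactate.** If resting lactate correlates equally with the rise at baseline and at the visit, and the variance of the rise is stable, its covariance with the difference of the two rises is zero. Adjusting for it then removes nothing. To relax this, 204 assumed covariance settings for rest and exercise lactate were examined:
- Resting lactate alone left 0.82 to 1.00 of the unadjusted variance (median 0.98).
- Adding baseline D beside resting lactate gave 0.65 to 1.00 of the planned model's variance (median 0.85).
- Replacing resting lactate with baseline D gave 0.65 to 1.18 (median 0.85), and was worse than planned in 17 of the 204 settings (8%).

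A simulation with 64 patients (eight doses of 6, placebo 16) assumed equal correlations over time for rest and exercise. Resting lactate alone gave about 1.01 of the unadjusted variance. With baseline D added as well, the ratios to unadjusted were 0.625, 0.762, 0.876 and 0.971 at correlations 0.2, 0.5, 0.7 and 0.9.

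**Visit 0.** SAP 6.3.3 and 6.3.4 list analysis visit 0 among those used. The double difference is zero there for every patient. If those rows are fitted, a baseline slope shared across weeks is pulled toward zero and the adjustment is lost.

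**The case against.** **Exploratory status.** SAP 6.3 labels p-values descriptive, SAP 3.5 applies no multiplicity adjustment, and SAP 1.3 does not expect Part 1 to characterise efficacy or pharmacodynamics fully. No 5% test decides anything here, so power is the wrong yardstick. This stands, and the effect is expressed above as interval width.

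**Dose selection.** A reader might infer that Part 2 doses would be chosen from these wider intervals. The documents do not say so. SAP 1 places the described analyses after the Part 1 lock, for the study report, while Protocol 7.1 has the sponsor selecting doses as cohorts open. SAP 2.2 allows earlier analyses to plan Part 2, but does not say they use this code.

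**Resting lactate as the wrong covariate.** A reader might conclude that it should be removed. SAP 3.4 names baseline resting lactate of 2.0 mM or below as a subgroup of interest, so it has a rationale. In the assumed settings it removed up to 18% of the variance, and swapping it out sometimes did worse. The supportable claim is that it is generally insufficient alone.

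**Pharmacodynamic label.** It fits lactate. The protocol does not list submaximal heart rate as pharmacodynamic.

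**Few patients.** Protocol 9.9.25 limits the test to selected sites, and the number of patients is not given. With very few, the gain can vanish, as the 16-patient case shows. This stands.

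**Imbalance is visible.** The baseline difference between rest and 30 minutes is to be summarised, so a 30-minute imbalance could be seen. Seeing it does not remove it from the estimate.

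**Overlap.** The heart-rate model inherits the covariate-free form of the primary model, so that half is related to the absence of a covariate for peak work. The lactate half is separate, because a covariate was chosen there.

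**Conclusion.** The point holds as a precision improvement to exploratory models. Neither model adjusts for the baseline of its own response, and the SAP gives no reason. SAP 3.3 does not rule the adjustment out, and SAP 6.3 already adjusts lactate.

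With equal variances, heart-rate residual variance falls by about 40%, 25% or 10% at assumed ρ of 0.2, 0.5 or 0.8. Intervals narrow by about 23%, 13% or 5%. The lactate gain is usually similar or smaller. It is negligible at ρ of about 0.9 or above, or with very few patients at the selected sites. These sizes rest on assumed correlations; the documents fix only the direction.

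It should not be read as a type I error problem or systematic bias. Under randomisation the planned contrasts are unbiased, and what improves is their width and their sensitivity to chance baseline imbalance.

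**What to change.** In SAP 6.3, 6.3.3 and 6.3.4, before the Part 1 lock:

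1. Fit post-baseline visits only. Drop analysis visit 0 as a response. Visit 8 should also leave the list, because no submaximal test is scheduled at Week 8.
2. Add time to the CLASS statement. It is missing, although the REPEATED and LSMEANS statements use it.
3. Use `model resp = trt*time*week base_delta*time*week / s`, where `base_delta` is the baseline value at the same minute minus baseline rest. This gives one slope per minute and week.
4. For lactate, keep `baseline_resting_lactate` in the same statement.

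The cost is SAP wording, a few lines of code and a few degrees of freedom: six slopes for three minutes at two visits, with about 2% on the variance of a contrast at 64 patients and more if few patients are tested. No patient is lost, since anyone without a baseline value at a given minute already has no response at that minute.

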## 6.3.1 Other Maximal Exercise Testing Measures (including Oxygen Utilization)

Various parameters in addition to peak work are assessed during maximal exercise testing, as listed below in Table 2.

Table 2: Maximal Exercise Testing Measures

Parameter	At Rest (Prior to Test)	At Maximal Work (End of Test)				
Expired Air Gas Volume (VeBTPS) (L/min) a	x	X				
Cardiac Output ( L/min ) a	X	X				
Heart Rate ( bpm ) a	X	X				
Oxygen Saturation (SpO2) (%)	X	X				
Diastolic Blood Pressure ( mmHg ) a	X	X				
Systolic Blood Pressure ( mmHg ) a	X	X				
Carbon Dioxide Production (VCO 2 ) ( mL/kg/min ) a, b	X	X				
Oxygen Consumption (VO 2 ) ( mL/kg/min ) a, b	X	X				
Arteriovenous Oxygen Difference (a-VO2diff) (mLO2/dlQ) a	X	X				
Respiratory Exchange Ratio	X	X				
Borg		X				
Leg Effort Rating of Perceived Exertion		X				
Exercise Duration ( min )		х				
Maximal work ( W/kg )		Х				
Maximal workload ( W )		х				
O2 pulse ( % ) c		X				
Observed values and difference between resting and neak performance for these parameters will be summarized at						

<sup>aObserved values and difference between resting and peak performance for these parameters will be summarized at baseline and at each timepoint.

For parameters measured at resting and at the end of the maximal exercise test, the change from resting and the change from baseline should be calculated.

The change from resting (delta) for parameters measured at resting and at the end of the maximal exercise test is defined as:

Delta = Parameter at maximal work - Parameter at resting

The change from baseline is defined for parameters measured at resting and at the end of the maximal exercise test is defined as:

b Analysis of VO2 and VCO2 will be performed using adjustments for weight at the visit week in which the maximal exercise test was performed, such that VO2 and VCO2 are in units of mL/kg/min

<sup>c O2 pulse will be calculated for analysis: O2 pulse = (Maximal\_VO2 (in units of mL/min)\*1000)/Maximal\_HR)

Change from baseline in Delta= [Parameter at maximal work(At Visit X) - Parameter at resting(At Visit X)] - [Parameter at maximal work(At Baseline) - Parameter at resting(At Baseline)]

Observed values and difference between resting and peak performance for these parameters will be summarized at baseline and at each timepoint. For all assessments, each parameter will be summarized at baseline and at each time point along with the change from baseline by treatment. For parameters measured at resting and at the end of the maximal exercise test [VeBTPS, cardiac output, heart rate, VO2 (L/min) and VO2 (ml/mg/min), VCO2 (L/min) and VCO2 (ml/mg/min), diastolic blood pressure, systolic blood pressure, a-VO2diff, and SPO2 (%)], the change from resting and the change from baseline should be calculated.

The change from resting (delta) for parameters measured at resting and at the end of the maximal exercise test is defined as:

Delta = Parameter at maximal work - Parameter at resting

The change from baseline is defined for parameters measured at resting and at the end of the maximal exercise test is defined as:

Change from baseline in Delta= [Parameter at maximal work(At Visit X) - Parameter at resting(At Visit X)] - [Parameter at maximal work(At Baseline) - Parameter at resting(At Baseline)]

Only summary statistics will be provided.

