#### 6. EFFICACY ANALYSIS

Primary analysis of the efficacy data will be based on the full analysis set, which will include all patients enrolled in Part 1 of the study. Analyses will be performed for each RTA 408 dose level. Summary statistics for observed values, change from baseline, and percent change from baseline (including 95% CI and quartiles) will be presented by randomized treatment group.

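### The O2 pulse formula in SAP Table 2 takes VO2 in mL/min and also multiplies by 1000, so its values are 1000 times too large as written, and the row is labelled as a percentage

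*SAP*

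**What the plan says.** SAP Section 6.3.1, Table 2, lists O2 pulse among the maximal exercise measures and puts a percent sign where the unit belongs. Footnote c is the only definition of O2 pulse in either document. It takes maximal VO2 "in units of mL/min", multiplies by 1000 and divides by maximal heart rate. Heart rate is in beats per minute in the same table ("Heart Rate ( bpm").

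The section uses other units for VO2 as well. Footnote b says that VO2 and VCO2 for analysis "are in units of mL/kg/min". The parameter list after the table has "VO 2 (L/min) and VO 2 (ml/mg/min".

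On reporting, Section 6.3.1 requires that "each parameter will be summarized at baseline and at each time point along with the change from baseline by treatment", and closes with "Only summary statistics will be provided". Section 6 more generally plans "Summary statistics for observed values, change from baseline, and percent change from baseline", with 95% confidence intervals and quartiles.

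**The concern.** A derivation rule in a SAP should give the same number to any programmer who follows it. This one does not agree with itself, because its input unit and its conversion factor cannot both be right if the result is to be O2 pulse in mL/beat. The factor of 1000 converts litres to millilitres, so applying it to a value already in millilitres converts twice.

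The row label does not settle the matter. A percentage needs a denominator such as a predicted value, and neither document supplies one for O2 pulse. The protocol does not define the quantity at all, and SAP Section 1 makes the SAP the governing text for analyses.

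At stake is the correctness of one descriptive table. Coded literally, the observed values, their SDs and confidence limits, and the absolute changes from baseline would be reported in the wrong magnitude and under a meaningless unit.

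**Working it through.** The SAP gives no numerical O2 pulse value to reproduce, so the check is one of units, followed by examples.

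**Inputs from SAP Section 6.3.1**

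- VO2 input unit in footnote c: mL/min
- Factor in footnote c: 1000
- Divisor: maximal heart rate, in beats/min (Table 2)
- Row label: percent
- Units for VO2 elsewhere in the section: mL/kg/min (Table 2 and footnote b) and L/min (parameter list)

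**Units under three readings**

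1. As written: (mL/min × 1000) ÷ (beats/min) = 1000 × mL/beat. Read as mL/beat, the number is 1000 times too large.
2. Factor deleted, input kept: (mL/min) ÷ (beats/min) = mL/beat.
3. Factor kept, input in L/min: (L/min × 1000) ÷ (beats/min) = mL/beat.

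Readings 2 and 3 give identical numbers. The ratio of reading 1 to either of them is 1000 for every VO2 and every heart rate.

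**Examples** (VO2 and heart rate are assumed; neither document gives values)

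| VO2, mL/min | Heart rate, bpm | VO2 ÷ HR, mL/beat | As written |
|---|---|---|---|
| 600 | 130 | 600/130 = 4.62 | 600 × 1000/130 = 4615 |
| 1200 | 150 | 1200/150 = 8.00 | 1200 × 1000/150 = 8000 |
| 2000 | 170 | 2000/170 = 11.76 | 2000 × 1000/170 = 11765 |

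With the middle case entered in litres, 1.2 × 1000/150 = 8.0, so the formula is right for L/min.

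Summary statistics scale by the same constant. The mean (SD) of the three values is 8.13 (3.58) mL/beat, against 8127 (3576) as written.

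**Change from baseline.** Suppose VO2 rises from 1200 to 1320 mL/min at 150 bpm.

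- Correct scale: 1320/150 − 1200/150 = 8.8 − 8.0 = +0.8 mL/beat
- As written: 8800 − 8000 = +800
- Percent change: 0.8/8.0 = 800/8000 = +10% either way

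The constant cancels in percent change and in relative differences between groups. It does not cancel in levels, SDs, confidence limits or absolute changes.

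**The second unit slip.** The parameter list prints "ml/mg/min), diastolic blood pressure, systolic blood pressure" for VO2, and the same unit for VCO2. Footnote b and Tables 2 and 4 have mL/kg/min. This is a typing error and carries no weight in the conclusion.

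**The case against.** The strongest reply is that the author probably meant VO2 in L/min. L/min appears in the parameter list of the same section, footnote c is the only place there that gives VO2 in mL/min, and 1000 is exactly the conversion from L/min. If the stored variable is in L/min and the programmer uses it directly, every reported value is correct and only the words in the footnote are wrong. To produce the thousandfold error, someone would have to hold VO2 in mL/min and then apply the factor. This may well be how the slip arose. But the footnote attaches mL/min to the input of the multiplication, nothing elsewhere corrects it, and the stored unit is not documented. It also does nothing for the percent label.

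A second point is that the SAP never names mL/beat, so calling the result too large rests on an inferred target unit. Strictly, the printed formula yields microlitres per beat. That is true, but mL/beat follows directly from the stated units once the extra factor is removed, and the absence of any valid output unit is part of the defect.

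The formula as extracted also has two opening and three closing parentheses, which may come from the PDF reading. The unit, the factor and the label are all legible, and the finding does not depend on the parentheses.

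Finally, a thousandfold error would be conspicuous in the first output and easily reversed. That stands, and it is one reason the point is minor.

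**Conclusion.** The concern holds. As written, footnote c gives exactly 1000 times O2 pulse in mL/beat, and the percent label is wrong on any reading. Which element of the formula is mistaken cannot be told from the documents: if VO2 is stored in mL/min, the factor is wrong; if it is stored in L/min, the stated input unit is wrong.

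The constant of 1000 follows from the units alone. Only the illustrative VO2 and heart rate values are assumed.

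The severity is minor. O2 pulse is not named in the endpoint list of SAP Section 2.3.1, and Section 6.3.1 restricts these measures to descriptive summaries. Percent change and relative comparisons are unaffected, and neither peak work nor six-minute walk distance uses this quantity.

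**What to change.** - In footnote c, either delete the factor of 1000 and keep the input as mL/min, or keep the factor and state the input as L/min. Choose whichever matches the stored VO2 variable, and name that variable and its unit in the footnote.
- In Table 2, label the O2 pulse row mL/beat instead of percent.
- As an editorial correction, change ml/mg/min to mL/kg/min for VO2 and VCO2 in the parameter list of Section 6.3.1.

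The cost is text edits to one footnote, one row label and one unit in a list. Whether any program code must change depends on the stored unit of VO2, which the documents do not show.
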